4.4.2 Dosage, Administration, and Compliance

4.4.2.1 RO5459072 and Placebo

Patients will be randomly assigned to one of two possible blinded study drug treatments:

- 100 mg RO5459072 (2 x F03 capsules) b.i.d. with food for 12 weeks.
- Placebo (2 x F04 capsules) b.i.d. with food for 12 weeks.

Study drugs are to be taken orally twice daily (b.i.d.) with food, i.e., with breakfast in the morning and a meal in the evening, for 12 weeks. Patients should start study drug treatment one day after the baseline visit. Capsules should be swallowed whole.

The qualified individual responsible for dispensing the study drug will allocate drug supplies according to the assigned patient randomization number. This individual will write the date dispensed and subject number on the Drug Dispensing Form. This individual will also record the study drug MEDNO received by each subject during the study.

Accountability and subject compliance will be assessed by maintaining adequate study drug dispensing records. The Investigator is responsible for ensuring that dosing is administered in compliance with the protocol. Delegation of this task must be clearly documented and approved by the Investigator.

4.4.3 Investigational Medicinal Product Accountability

All IMPs required for completion of this study (RO5459072 and placebo) will be provided by the Sponsor. The investigational site will acknowledge receipt of IMPs, to confirm the shipment condition and content. Any damaged shipments will be replaced.

The Investigator is responsible for the control of drugs under investigation. Adequate records of the receipt (e.g., Drug Receipt Record) and disposition (e.g., Drug Dispensing Log) of the study drug must be maintained. The Drug Dispensing Log must be kept current and should contain the following information:

- The identification of the patient to whom the study drug was dispensed (for example patient initials and date of birth).
- The date(s), quantity of the study drug dispensed to the patient.
- The date(s) and quantity of the study drug returned by the patient.
- All records and drug supplies must be available for inspection by the Roche Monitor at every monitoring visit.

IMPs will either be disposed of at the study site according to the study site's institutional standard operating procedure or returned to the Sponsor with the appropriate documentation. The site's method of IMP destruction must be agreed upon by the

Sponsor. Local or institutional regulations may require immediate destruction of used investigational medicinal product for safety reasons. In these cases, it may be acceptable for investigational study site staff to destroy dispensed investigational product before a monitoring inspection provided that source document verification is performed on the remaining inventory and reconciled against the documentation of quantity shipped, dispensed, returned, destroyed and provided that adequate storage and integrity of drug has been confirmed.

The site must obtain written authorization from the Sponsor before any IMP is destroyed, and IMP destruction must be documented on the appropriate form.

Written documentation of destruction must contain the following:

- Identity medication number (MEDNO) of investigational product[s] destroyed.
- Quantity of investigational product[s] destroyed.
- Date of destruction.
- Method of destruction.
- Name and signature of responsible person [or company] who destroyed investigational product[s].

Accurate records of all IMPs received at, dispensed from, returned to, and disposed of by the study site should be recorded on the Drug Inventory Log.

4.4.4 Post-Trial Access to RO5459072

RO5459072 will not be provided to participants after conclusion of the study.

4.5 CONCOMITANT THERAPY AND FOOD

4.5.1 Permitted Therapy

In addition to the study drug treatment, patients may continue to concomitantly use existing treatments for Sjögren's syndrome. With exception of the prohibited therapies described in Section 4.5.2, systemic immunomodulatory therapy (e.g., hydroxychloroquine), low dose corticosteroids (≤ 7.5 mg prednisone equivalent dose per day), or low dose methotrexate, or topically administered immunosuppressive agents (e.g., cyclosporine eye drops) are permissible provided the patient has been on a stable dose for ≥ 2 months prior to screening and the dose is expected to remain unchanged during the study. Similarly patients on non-steroidal anti-inflammatory drugs (NSAIDs), antidepressants, or pilocarpine must also have been on a stable dose for 4 weeks prior to screening and be expected to remain on this dose throughout the study. If any of these drugs have been discontinued recently, patients must be off drug for at least 8 weeks before screening.

All medications (prescription and over-the-counter [OTC]) taken within 30 days of study screening visit, until the follow-up visit, will be recorded on the appropriate eCRF. The

dose and/or frequency of use of selected medications commonly prescribed to patients with Sjögren's syndrome will be specifically captured in the eCRF.

4.5.2 Prohibited Therapy

Use of concomitant therapies which systemically suppress the immune system are not permitted during the study. Prohibited therapies are:

- Corticosteroid therapy exceeding 7.5 mg prednisone equivalent per day (see [Appendix 3](#)).
- Anti-CD20 therapy (e.g., rituximab) or other B cell-depleting therapy within 6 months of screening.
- Immunosuppressant therapy (e.g., abatacept, azathioprine, ciclosporin, etanercept, tofacitinib). Low dose methotrexate treatment (oral doses \leq 20 mg weekly) is, however, permitted.
- Cyclophosphamide.

Pilocarpine or drugs with similar pharmacological action should not be used within 12 hours prior to an assessment visit.

Because RO5459072 is a substrate of CYP3A4 and P-gp, other prohibited medications are:

- Moderate or potent inhibitors of CYP3A4 (e.g., itraconazole, erythromycin, nefazodone).
- Strong inducers of CYP3A4 (e.g., rifampicin, carbamazepine).
- *Sensitive substrates of CYP3A4 with a narrow therapeutic index (e.g., alfentanil, colchicine, ethosuxamide, fentanyl, and pimozide).*
- Strong inhibitors of the transporter P-glycoprotein (P-gp) (e.g., quinidine, clarithromycin).

A full list of prohibited concomitant medications is provided in [Appendix 4](#).

RO5459072 weakly induces CYP3A4 activity in vitro. RO5459072 treatment therefore has the theoretical potential to cause a small decrease in exposure of concomitantly administered CYP3A4 substrates. For this reason, caution is advised when initiating study drug treatment in individuals already established on a stable dose of a CYP3A4 substrate, or starting dosing with a CYP3A4 substrate in individuals receiving study drug treatment. See Section [4.2.2](#) regarding use of hormonal contraception.

In vitro data indicate that RO5459072 weakly inhibits the transport of substrates of MDR1 (P-gp), OATP1B1 and MATE2-K transporters. The potential for RO5459072 to alter the pharmacokinetics of substrates of these transporters (e.g., digoxin, pravastatin, metformin, etc) in vivo cannot be entirely discounted. Therefore, caution is advised when

administering study drug treatment together with medications known to be substrates of these transporters.

RO5459072 was found to induce CYP2B6 expression and enzyme activity in vitro but its M1 metabolite was also found to be a moderate inhibitor of CYP2B6 in vitro. It is therefore possible that RO5459072 treatment may lead to changes in exposure of concomitant medications which are predominantly metabolized by CYP2B6. For this reason, caution is advised when administering RO5459072 treatment together with medications known to be sensitive substrates of CYP2B6 (e.g., efavirenz, bupropion).

4.5.3 Vaccination

Investigators should be aware of the theoretical potential for study drug treatment to impair vaccine efficacy. Investigators should therefore follow local guidelines and standards of care for immunization of individuals receiving immunosuppressant therapies. The use of live vaccines is not recommended.

4.5.4 Food

Study drugs are to be taken with food. Food and beverages containing grapefruit or grapefruit juice should be avoided during the study because of the potential effects on CYP3A4 activity.

4.5.5 Contraception

Embryo-fetal development studies identified a teratogenic potential of RO5459072. Enrolment in the study is therefore contingent on agreement to comply with measures to prevent pregnancy. All women are required to have a negative pregnancy test at screening and baseline and any woman who becomes pregnant should be immediately withdrawn from the study (see Sections [4.7.1](#) and [5.4.3](#)).

Women of childbearing potential must agree to remain abstinent (refrain from heterosexual intercourse) or use a contraception method that results in a failure rate of < 1% per year, during the treatment period and for at least 28 days after the last dose of study drug.

- Examples of non-hormonal contraceptive methods with a failure rate of < 1% per year include bilateral tubal ligation, male sterilization, and copper intra uterine devices.
- Examples of hormonal contraceptive methods with a failure rate of < 1% per year include established, proper use of hormonal contraceptives that inhibit ovulation, hormone-releasing intra-uterine devices. However, because of the theoretical potential for drug-drug interactions which might impair the efficacy of hormonal contraception, these must be supplemented with a barrier method such as male or female condom with spermicide.

A woman is considered not to be of childbearing potential if she is post-menopausal (≥ 12 months of non-therapy-induced amenorrhea, with no identified cause other than menopause) or has undergone surgical sterilization (removal of ovaries and/or uterus).

Men with female partners of childbearing potential or pregnant female partners, men must remain abstinent (refrain from heterosexual intercourse) or use a condom during the treatment period and for at least 28 days after the last dose of study drug to avoid exposing the embryo. All men must refrain from donating sperm during the treatment period and for at least 28 days after the last dose of study drug.

The reliability of sexual abstinence should be evaluated in relation to the duration of the clinical trial and the preferred and usual lifestyle of the patient. Periodic abstinence (e.g., calendar, ovulation, symptothermal, or post ovulation methods) and withdrawal are not acceptable methods of contraception.

4.6 STUDY ASSESSMENTS

4.6.1 Description of Study Assessments

All examinations listed below will be performed according to the schedule of assessments outlined in [Appendix 1](#). Instruction manuals and supply kits will be provided for all central laboratory assessments.

4.6.1.1 Medical History and Demographic Data

Medical history includes clinically significant diseases, all surgeries, reproductive status, smoking history, use of alcohol and drugs of abuse and all concomitant medications (e.g., prescription drugs, OTCs, herbal or homeopathic remedies, nutritional supplements) used by the patient within 30 days prior to the screening visit.

Demographic data will include age, sex, and self-reported race/ethnicity.

4.6.1.2 Physical Examinations

Any abnormality identified at baseline should be recorded on the General Medical History and Baseline Conditions eCRF.

At subsequent visits (or as clinically indicated), limited, symptom-directed physical examinations should be performed. Changes from baseline abnormalities should be recorded in patient's notes. New or worsened clinically significant abnormalities should be recorded as adverse events on the Adverse Event eCRF.

A complete physical examination should include an evaluation of the head, eyes, ears, nose, throat, neck and lymph nodes, and the cardiovascular, dermatological, musculoskeletal, respiratory, gastrointestinal, genitourinary, and neurological systems.

A physical examination will include careful attention to areas of known and possible malignancy.

4.6.1.3 Disease-Specific Assessments

4.6.1.3.1 ESSDAI

EULAR Sjögren's Syndrome Disease Activity Index (ESSDAI) will be employed to assess disease activity at baseline and during the treatment phase. The ESSDAI is a physician-assessed disease activity index for primary Sjögren's syndrome developed by the EULAR consortium ([Seror et al 2010](#); [Seror et al 2015](#)). It consists of 44 items in 12 organ-specific 'domains' contributing to disease activity (constitutional, lymphadenopathy, articular, muscular, cutaneous, glandular, pulmonary, renal, peripheral nervous system [PNS], central nervous system [CNS], hematological, biological). Each domain is assessed for activity level (i.e., no, low, moderate, high) and assigned a numerical score based on pre-determined weighting of each individual domain. An overall score is then calculated as the sum of all individual weighted domain scores.

4.6.1.3.2 ESSPRI

EULAR Sjögren's Syndrome Patient Reported Index (ESSPRI) will be used to assess Sjögren's syndrome symptom severity at baseline and during the treatment phase. The ESSPRI is a patient-reported, subjective symptom index for primary Sjögren's syndrome developed by the EULAR consortium ([Seror et al 2011](#), [Seror et al 2015](#)). It consists of three questions covering the cardinal symptoms of Sjögren's syndrome: dryness, fatigue and pain (articular and/or muscular). Each domain scored on scale of 0-10, and an overall score is calculated as the mean of the three individual domains where all domains carry the same weight.

A clinically relevant change in ESSPRI score is defined as an absolute decrease of ≥ 1 point ([Seror et al 2014](#)).

4.6.1.3.3 SF-36 V2 (Acute Version)

The Short Form 36 Health Survey (SF-36 V2) will be used to assess health-related quality of life at baseline and at on-treatment visits. The SF-36 consists of 36 questions covering 8 domains (general health, physical functioning, role-functioning physical, bodily pain, social functioning, role-functioning emotional, mental health and vitality), with each domain scored on a scale 0-100 ([Ware et al 1993](#)). The acute version has a 1-week recall period, asking patients to consider the past week in responding to questions.

4.6.1.3.4 Salivary and lacrimal gland function

- Mechanically Stimulated Salivary Flow

Stimulated salivary flow will be measured at baseline and at on-treatment visits using a mechanical stimulation method. The test should be performed at a similar time of day at each visit and conducted under standard conditions; patients should refrain from oral hygiene procedures, smoking, eating and drinking for at least 2 hours before the test and be seated in an upright position. Patients will be provided with a piece of neutral wax, paraffin, silicone, unflavored chewing gum, or similar chewable, unflavored, non-absorbent material and instructed to chew for a period of 5 minutes. Saliva will be

collected into a pre-weighed collecting container. The container is then re-weighed to determine the weight of saliva. The stimulated salivary flow rate is calculated assuming a specific gravity of 1 (i.e., 1 mL saliva = 1 g) and expressed in mL per minute. The sample will be used for biomarker measurements. The samples can be frozen (for further details, see the Laboratory Manual).

- Tear production

Un-stimulated tear production rate will be measured from both eyes (without the use of analgesics/ anesthetic drops) at baseline and at on-treatment visits using the Schirmer method. A thin strip of filter paper (Schirmer strip, e.g., 35 x 5 mm) will be placed at the junction of the lateral and middle thirds of the lower eyelid of each eye and the eyes should be gently closed. The strips will be left in place for 5 *minutes* so that tear fluid is absorbed. The maximum length of wetting along the strip at the end of the test period will be measured and recorded in millimeters. The sample will be used for biomarker assessments too.

4.6.1.4 Laboratory Assessments

Laboratory safety tests shall be collected at visits specified in the Schedule of Assessments ([Appendix 1](#)). On each occasion patients must have fasted for at least 4 h before sampling.

Additional blood or urine samples may be taken at the discretion of the Investigator if the results of any test fall outside the reference ranges, or clinical symptoms necessitate additional testing to monitor patient's safety. Where the clinical significance of abnormal lab results is considered uncertain, screening lab tests may be repeated before randomization to confirm eligibility. If there is an alternative explanation for a positive urine or blood test for drugs of abuse, e.g., previous occasional intake of a medication or food containing for example codeine, benzodiazepines or opiates, the test could be repeated to confirm washout.

In the event of unexplained abnormal clinically significant laboratory test values, the tests should be repeated immediately and followed up until they have returned to the normal range and/or an adequate explanation of the abnormality is found. Results of clinical laboratory testing will be recorded on the eCRF or be received as electronically produced laboratory reports submitted directly from the central laboratory. Situations may arise when local laboratories are utilized such as for safety labs. In these cases, reference ranges must be submitted where applicable.

With the exception of the urine pregnancy and ESR tests, which will be locally assessed, the samples for the following laboratory tests will be sent to the central laboratory for analysis:

- **Hematology:** Hemoglobin, hematocrit, platelet count, red blood cell (RBC) count, mean corpuscular volume, absolute reticulocyte count, total and differential

leucocyte (WBC) absolute count (neutrophils, eosinophils, lymphocytes, monocytes and basophils).

- **Blood chemistry:** Albumin, alkaline phosphatase (ALP), alanine aminotransferase (ALT), aspartate aminotransferase (AST), *bicarbonate*, C-reactive protein (CRP), calcium, chloride, creatinine phosphokinase (CPK), gamma-glutamyl transferase (GGT), glucose, phosphate, potassium, creatinine, sodium, total bilirubin, total protein, troponin, urea, *complement (C3 and C4)*.
- **Coagulation:** activated partial thromboplastin time (aPTT), prothrombin time (PT)
- **Lipids:** High-density lipoprotein-cholesterol (HDL-C), low-density lipoprotein cholesterol (LDL-C), triglycerides, total cholesterol.
- **Urinalysis** A midstream urine specimen will be collected for dipstick analysis of protein, blood, glucose, and pH.
- At Screening only: HIV (specific tests HIV-1 antibody, HIV-1/2 antibody, HIV-2 antibody), hepatitis B surface antigen (HBsAg), total hepatitis B core antibody (HBcAb), hepatitis C virus (HCV) antibody, *tuberculosis testing*.
- **Pregnancy test:** All women (including those who have had a tubal ligation) will have a serum pregnancy test at screening and at baseline. A urine pregnancy test will also be done at baseline prior to randomization. Women of childbearing potential will have serum and urine pregnancy tests at all subsequent visits (see SoA table, [Appendix 1](#)).

4.6.1.5 Pharmacokinetic Assessments

Blood samples for measurement of plasma concentrations of RO5459072 using a validated assay (and its metabolites as appropriate, in an exploratory manner) will be collected at visits specified in the SoA ([Appendix 1](#)). Samples will be sent to a central laboratory for analysis. The date and time of each sample collection will be recorded in the eCRF.

Plasma concentrations of RO5459072 will be measured by a specific and validated liquid chromatography-tandem mass spectrometry (LC-MS/MS) method. Metabolites may also be measured in exploratory manner using qualified analytical methods.

The plasma concentration data will be pooled with data from other studies (e.g., [WP29542](#) and [BP29772](#)) for population pharmacokinetic and pharmacokinetic/pharmacodynamic modelling. The results of that population modelling will be reported separately.

4.6.1.6 Pharmacodynamic Assessments

Samples for the pharmacodynamics assessments will be either locally analyzed, sent to one or several central laboratories or to the Sponsor for analysis.

Pharmacodynamic assessments will include the measurement of tear flow rate using the Schirmer's test, stimulated salivary flow rate, serum auto-antibody titers, ESR, collection

of samples for measurement of circulating numbers of sub-populations of white blood cells, biomarkers connected to Sjögren's syndrome and extracellular matrix degradation. Cathepsin S mass and activity will be measured in plasma, tears and saliva samples (please see SoA, [Appendix 1](#)). Auto-antibody titers will also be measured at screening in order to assess eligibility for the study.

Based on continuous analysis of the data in this study from the samples collected, samples not considered to be critical for safety may be amended or stopped during study conduct.

Auto-antibodies (anti-SSA/SSB)

Serum will be collected for the determination of anti-SSA/SSB autoantibodies as indicated in the SoA ([Appendix 1](#)). These measurements will include anti-SSA, anti-SSB, ANA, and rheumatoid factor, as well as total IgG, *IgM* and cryoglobulins.

Immunophenotyping

Whole blood samples will be collected to quantify white blood cell counts by flow cytometry (CD4+ T cells and follicular T helper cells, B cell subsets and natural killer [NK] cells) at the visits indicated in the SoA ([Appendix 1](#)). Sub-populations of white blood cells will be counted by FACS immunophenotyping of cell surface markers and may include TBNK/monocytes, T_H and T_{FH} cells and B cells.

Soluble Biomarker Assessments

Plasma samples - Samples for measurement of biomarkers connected to Sjögren's syndrome and extracellular matrix degradation will be collected at specified visits as indicated in the SoA ([Appendix 1](#)). Biomarkers to be measured will include β 2-microglobulin, cytokines (including - but not limited to - BAFF, IL-4, IL-6 and IL-10), beta-hydroxycholesterol and desmosine.

For sampling procedures, storage conditions, and shipment instructions, refer to the separate central laboratory documentation.

Cathepsin S Mass and Activity

Plasma samples - Samples for measurement of cathepsin S mass and activity will be collected at specified visits as indicated in the SoA ([Appendix 1](#)).

Saliva and tear samples – Cathepsin S mass and activity will be measured in saliva and tear fluids collected as part of pharmacodynamic assessments of salivary and lacrimal gland flow (see Section [4.6.1.3](#)).

Erythrocyte Sedimentation Ratio

Samples for determining the ESR value and inflammation related to Sjögren's syndrome will be collected at specified visits as indicated in the SoA ([Appendix 1](#)).

mRNA Sampling

A whole blood sample will be collected for mRNA extraction as indicated in the SoA ([Appendix 1](#)). The mRNA may be used to measure gene expression changes related to interferon response including, but not limited, to MxA.

4.6.1.7 Clinical Genotyping

A whole blood sample will be collected for DNA extraction, as indicated in the SoA ([Appendix 1](#)). The DNA may be used for genotyping of alleles in genes encoding transporters and drug metabolizing enzymes (e.g., CYP3A4, CYP3A5) and transporters (e.g., MDR1), human leukocyte antigens (i.e., HLA gene family) and cathepsin S (CTSS). The DNA will be destroyed after analysis and the data arising from clinical genotyping will be subject to the confidentiality standards described in Section [8.4](#).

4.6.1.8 Electrocardiograms

Triplicate 12-lead ECG recordings (i.e., three useful ECGs without artifacts) will be obtained within approximately 2-5 minutes at each specified visits. The average of the three readings will be used to determine ECG intervals (e.g., PR, QRS, QT). Additional unscheduled ECGs should be performed in case of abnormalities and if clinical symptoms occur. Whenever possible, the same brand/model of a standard high-quality, high-fidelity electrocardiograph machine equipped with computer-based interval measurements should be used for each patient. The conditions should be as close as possible to the baseline ECG; this includes, but is not limited to, food intake, activity level, stressors and room temperature.

To minimize variability, it is important that patients be in a resting position (semi-recumbent) for ≥ 10 minutes prior to each ECG evaluation. Body position should be consistently maintained for each ECG evaluation to prevent changes in heart rate. Environmental distractions (e.g., television, radio, conversation) should be avoided during the pre-ECG resting period and during ECG recording. In some cases, it may be appropriate to repeat abnormal ECGs to rule out improper lead placement as contributing to the ECG abnormality.

For safety monitoring purposes, the Investigator or designee must review, sign, and date all ECG tracings. Paper or electronic copies will be kept as part of the patient's permanent study file at the site. If considered appropriate by Roche, ECGs may be analyzed retrospectively at a central laboratory.

ECG characteristics, including heart rate, QRS duration, and PR, and QT intervals, will be recorded on the eCRF. QTcF (Fridericia's correction) and RR will be calculated by the Sponsor/recorded on the eCRF. Changes in T-wave and U-wave morphology and overall ECG interpretation will be documented on the eCRF. T-wave information will be captured as normal or abnormal, U-wave information will be captured in two categories: absent/normal or abnormal.

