3.3.4 Safety Outcome Measures

The safety outcome measures for this study are as follows:

- The incidence and severity of AEs.
- The incidence of SAEs or withdrawals because of AEs.

- The incidence of out-of-reference-range values for vital signs and ECGs, and laboratory tests.
- Change from baseline in vital signs and ECGs, and laboratory tests by visit.

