6.5.2 Clinical Laboratory Test Results

All clinical laboratory data will be stored on the database in the units in which they were reported. Patients' listings and summary statistics at each assessment time will be presented using the International System of Units (SI units; *Système International d'Unités*). Laboratory data not reported in SI units will be converted to SI units before processing.

Laboratory test values will be presented by individual listings with flagging of values outside the normal ranges. Summary tables of change from baseline over time based on SI (Standard International) units will be displayed. Shifts in grade from baseline to the worst grade observed during treatment will be presented for selected laboratory parameters.

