6.5.4 ECG Data Analysis

ECG data will be presented by individual listings with flagging of values outside the normal ranges and flagging of marked abnormalities. In addition, the 12-lead triplicates will be averaged out. All analyses of QT data will be based on averages of the triplicate

measures at each scheduled time-point. These averages will be derived prior to any further data manipulation. Tabular summaries will be used, as appropriate.

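### Section 6.5.4 limits all QT analyses to scheduled triplicate averages, so a QT value out of range only on a symptom-triggered ECG between visits is listed but not counted in the QT incidence summary

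*Combined protocol and SAP*

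**What the plan says.** **Collection.** Section 4.6.1.8 schedules triplicate 12-lead ECGs and adds event-driven ones: "Additional unscheduled ECGs should be performed in case of abnormalities and if clinical symptoms occur". It does not say whether the extra ECGs must also be triplicate.

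**Outcomes.** Section 3.3.4 lists two ECG outcomes. One is "The incidence of out-of-reference-range values for vital signs and ECGs, and laboratory tests", with no restriction to scheduled visits. The other is change from baseline, which is explicitly by visit.

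**Analysis.** Section 6.5.4 first provides for listings: "ECG data will be presented by individual listings with flagging of values outside the normal ranges and flagging of marked abnormalities". It then sets the rule for QT in one sentence that runs across a page break and opens: "All analyses of QT data will be based on averages of the triplicate". The rest of that sentence ties the averages to the scheduled visits, and the one after it has them computed before the data are processed in any other way. The section names no worst post-baseline QT summary and gives no rule for unscheduled tracings.

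**Comparison.** For selected laboratory parameters, Section 6.5.2 does use the worst value on treatment: "Shifts in grade from baseline to the worst grade observed during treatment". No ECG section has a counterpart.

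**The concern.** By-visit means and incidence of abnormal values need different data. For a mean change at Week 6, the scheduled triplicate average is the right input: every patient contributes on the same terms, and averaging reduces noise. For the question of how many patients ever had an out-of-range QT, every post-baseline ECG is relevant, including those prompted by symptoms.

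Section 6.5.4 applies one rule to both questions. The protocol therefore asks sites to collect ECGs that the QT tables then have no place for. At stake is whether the QT part of a stated safety outcome is complete. With 35 patients per arm, a single patient can decide whether the table shows a case or none.

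**Working it through.** The plan gives no figure for QT (no expected rate, threshold count or power), so there is nothing to reproduce. The check is a comparison of sections, followed by one illustration.

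**1. Where each kind of QT value goes under Section 6.5.4 as written**

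- *Abnormal at a scheduled visit, then repeated.* The scheduled triplicate average stays in the analysis, so the patient is counted. Nothing is lost.
- *Out of range on a symptom-triggered ECG between visits, and also on a scheduled ECG.* The patient is counted through the scheduled value. Only a higher maximum could be missed.
- *Out of range only on a symptom-triggered ECG between visits.* The value is flagged in the listing. Under Section 5.1.1 it becomes an adverse event if the deterioration goes with symptoms or leads to a change in study or concomitant treatment or to discontinuation, and Section 6.5.1 then tabulates it. It does not enter the QT incidence, because all QT analyses use scheduled averages.
- *Non-QT findings (heart rate, PR, QRS, T- or U-wave).* The restricting sentence concerns QT data only and does not exclude them.

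The gap is the third case alone.

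**2. How much time lies between scheduled ECGs**

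Appendix 1 places on-treatment ECGs at Days 14, 42, 63 and 84, each ±7 days, plus follow-up and early termination.

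- Nominal gaps: 42 − 14 = 28 days; 63 − 42 = 21 days; 84 − 63 = 21 days.
- Longest gap the windows allow between Weeks 2 and 6: (42 + 7) − (14 − 7) = 42 days.

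There is room for an event-driven ECG between visits. The documents do not give its likely frequency.

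**3. Illustration**

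Inputs: 35 patients on active drug (Section 6.1), all assumed dosed. One patient is assumed to fall in the third case and none otherwise to have an out-of-range QT. Intervals are exact (Clopper-Pearson), two-sided 95%.

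- Counted: 1/35 = 2.9%. Lower limit 1 − 0.975^(1/35) = 0.0007, or 0.07%. The upper limit solves (1 − p)^34 × (1 + 34p) = 0.025, giving p = 0.149, or 14.9%.
- Not counted: 0/35 = 0%. Upper limit 1 − 0.025^(1/35) = 0.100, or 10.0%.

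The intervals overlap widely. What changes is whether the table shows a case.

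**The case against.** The strongest reply is that little is hidden. The listings in Section 6.5.4 are not limited to scheduled ECGs, Section 3.3.4 does not limit the incidence outcome either, and Section 6.5 has all safety parameters both listed and tabulated. The QT sentence could be read as a unit-of-analysis rule (average the triplicate first) rather than an exclusion. A symptomatic QT deterioration would often qualify as an adverse event. Section 4.6.1.8 also has the investigator review and sign every tracing.

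There are further points on that side:

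- The laboratory comparison covers only selected parameters and does not say whether unscheduled values count.
- Section 6.5 plans no formal safety testing.
- Section 6 defers details to a statistical analysis plan, and no further ECG rule appears in the text available.
- Prior evidence of QT risk is modest. The hERG IC20 is 25 µg/mL (Section 1.3.1.3) against a steady-state Cmax of 2.34 µg/mL (Section 3.2.1), a ratio of 25/2.34 = 10.7. Section 1.3.2.1 reports no dose-related ECG trend in the earlier studies.

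Most of this stands and limits the point to minor priority. It does not remove it. A listing or an adverse event table is not the QT incidence summary. The QT sentence says all analyses and names scheduled time-points, so a programmer following it would exclude the value. If the intention was only to average before analysis, or to let unscheduled values count, one sentence is needed to say so.

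**Conclusion.** The point holds in a limited form. The sections do not contradict each other. Section 6.5.4 states a rule that suits by-visit summaries but is too broad for the incidence outcome in Section 3.3.4. The affected case is a QT value out of range only on a symptom-triggered ECG between visits. Its frequency is unknown, and 1/35 versus 0/35 is illustrative. The conclusion assumes that Section 6.5.4 is applied literally and that no separate plan overrides it. It is a cheap improvement of minor priority.

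Three stronger readings might be inferred, and the documents do not support them:

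- *That the omitted ECGs are those most likely to show a drug effect, so QT safety is biased towards no signal.* No data in the documents bear on this, and the listing and adverse event routes remain open.
- *That central re-reading could selectively replace extreme values.* Section 4.6.1.8 says only that, if the sponsor considers it appropriate, "ECGs may be analyzed retrospectively at a central laboratory". Nothing says that only outliers would be re-read or that central values would replace site values.
- *That this is the first 12-week exposure to the drug.* Section 1.4.2 calls it the fourth human study but describes only two completed earlier ones. The duration of the remaining study is not given.

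**What to change.** In Section 6.5.4:

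- Confine the scheduled triplicate-average rule to QT values and changes from baseline summarised by visit.
- State that unscheduled post-baseline ECGs, using the mean of whatever readings are available, are included in each patient's worst post-baseline QTcF, in the maximum change from baseline, and in the counts of out-of-range and marked values.

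The cost is a few lines of text and one extra table. Visits, procedures and by-visit means stay as they are. The downside is that some unscheduled ECGs may be single tracings, so the per-patient maximum is slightly noisier than one built from triplicates alone.
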